6.7 Early Termination Visit

Participants who discontinue HCV treatment prior to treatment completion for medical or personal reasons will be given the option of being followed as per study schedule for risk assessments, lab monitoring, and ongoing optional PrEP and buprenorphine (if already initiated). Participants who discontinue PrEP or buprenorphine will continue to be monitored per the HCV study schedule, however will no longer have monitoring specific to PrEP or buprenorphine. The participant should have an end of treatment visit scheduled as soon as possible after all therapy is discontinued. The reason for any early termination will be documented.

7 Potential Risks and Benefits

7.1 Potential Risks

Given this investigation is centered on implementation of a novel model of care, the main risks are related to any blood draw outside of standard of care, and loss of confidential data.

The potential risks include risks of phlebotomy that include: pain, bruising, fainting and very rarely, infection. These risks will be minimized by having trained staff perform the procedure.

There is potential for loss of confidentiality, which will be minimized by providing privacy during study visits. In addition, all laboratory specimens, and research records will be coded by a number to maintain subject confidentiality. All paper records will be kept locked with limited access. Electronic data will be password protected and will not include participant names or contact details.

Risks from smartphones and GMA. Carrying and using the smartphone could be annoying or embarrassing to the study participant. The smartphone will be collecting personal

information and location, but this information will not be displayed on the phone and not linked to any of personal information/identifiers. A PIN code is needed to access the smartphone and the specific application that is used to provide data. Responses will regularly be transferred from the smartphone to secure password-protected computers located at the National Institute on Drug Abuse (NIDA), limiting the amount of information that is contained on the phone. The data does not contain information that could be used to identify participants. The data is transferred from phone to NIDA secure server.

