6.6 Optional Geographic Momentary Assessment

All enrolled subjects in Phase 2 (participants 101-200) will be offered participation in the Geographic Momentary Assessment (GMA), an optional, exploratory outcome through a research collaboration with the National Institute of Drug Abuse (NIDA) to further explore drug use, overdose, risky behaviors, and barriers to hepatitis C treatment and PrEP.

While many patients inducted and stabilized on buprenorphine or methadone reduce or eliminate opioid use, there remains a group of individuals who continue to use opioids despite opioid agonist therapy. Additionally, there are patients in treatment who continue to use drugs other than opioids including alcohol, marijuana, stimulants among others. These individuals remain at

risk for harm including overdose, acquiring or transmitting HIV, HCV, and other diseases, and poor adherence to medical treatment.

This NIDA-developed technology, GMA, combines Ecological Momentary Assessment (EMA), the collection of real-time in the field data via smartphones, with GPS of self-reported data on craving, drug use, and stressors collected daily in real time via a cell-phone based application (APPENDIX G). Using the smartphone's GPS log, we will collect data on participants' locations throughout the day to assess how changes in environment affect mood and activities. GMA overcomes the limitations of retrospective assessments, which may not adequately measure the dynamics of craving or accurately depict the relationships between craving and use (Tiffany & Wray, 2012; Kavanagh et al., 2013; Serre et al., 2015). The GPS receiver chipsets have become ubiquitous in smartphones and, by combining GPS information with information on the strength of signals obtained from cellular data networks and wireless internet data connections (i.e., assisted GPS), smartphones can provide accurate location information more quickly than standalone GPS units and in cases where GPS signals are attenuated (e.g., indoors, in urban areas with many tall buildings) (Zandbergen, 2009; Zandbergen & Barbeau, 2011).

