These assessments will be evaluated on an ongoing basis by Drs. [name] and [name] (sub-investigators on the protocol), who are nationally recognized experts in the field of GMA as it relates to substance use-disorder and drug craving. NIDA has been conducting GMA studies since 2005 and has collected data on over 850 study participants. The results of their work have been published in high-quality journals; the first paper was published in 2009 in Archives of General Psychiatry⁽³⁰⁻⁵⁷⁾. Recently NIDA used GMA to study the effects of clonidine on relapse to opioid use in patients receiving buprenorphine maintenance which was published in the American Journal of Psychiatry⁽⁴²⁾.

This exploratory outcome will parallel hepatitis C treatment and PrEP and buprenorphine/methadone treatment as indicated, without impacting the above listed research assessments or study visit schedule. Using cell phones with active data plans provided free to enrolled subjects for one year, subjects will be queried by an GMA-specific application four times per day from Day 0 – Week 24 and one-time daily from Week 25-48 to complete an assessment of drug use, craving, stress, and other social and behavioral factors as an in-depth risk assessment (see Appendix G). Subjects will have training on use of the GMA application on Day 0, and phones will be distributed. Subjects will then complete surveys on a daily basis and will return their cell phones at Week 48. These prompts will take between 5 and 8 minutes on average to complete, and will be associated with weekly remuneration if completed regularly (see section 11). Participants can briefly turn off the alerts if they are driving, showering, etc. Participants are otherwise instructed to respond, even if at work.

For participants enrolled in GMA, at their ANCHOR visits they will complete an Adherence Packet-4 at baseline. The Adherence packet-4 (APPENDIX I) consists of 4 questionnaires (total about 15 minutes) including:

1. **The Perceived Stress scale (PSS)** (Cohen et al., 1983) is a 14-item measure of self-rated stress levels and coping ability over the past month. Takes about 5 minutes (Appendix 37).

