Some blood samples may be stored for future analysis in this research study. These samples will be stored by the IHV researchers and may be used in future research to learn more about HCV and HIV, the immune system and/or other related medical conditions. The blood will be used over time to gain a better understanding of the pathogenesis of HCV and HIV. Genetic testing will be performed. Different analytical and laboratory methods will be employed including but not limited to: PCR, ELISA, ELISPOT and immunohistochemistry; RNA/DNA, cytokine and antibody quantitation; viral particle detection and identification of genetic markers. The consent will include language for specimen storage.

8.2 Storage:

Samples will be kept in secure facilities with limited access. Samples and data will be stored using a unique identifier. Only investigators and study staff will have access to the samples and data.

GMA Data - Electronic data will be stored on secure password-protected computers. UMB has an executed Collaboration Agreement dated 5/1/18 with the National Institute on Drug Abuse (NIDA), National Institutes of Health (NIH) and will share some data as specified in the agreement with our scientific research partners at NIH. There will be no participant identifiers in the shared data.

8.3 Tracking:

Extra blood samples will be stored using a unique identifier that only the study team can trace back to the participants. These stored samples as well as a linkage file will be maintained in a database that will be managed by the Investigators and/or Study Coordinators and will be maintained on the IHV server. This database will also be stored on the password-protected computer of the Lead-Investigator/Study Coordinator in an encrypted and/or password-coded file.

8.4 Disposition at the Completion of the Protocol:

At the completion of the protocol (termination), samples and data will either be destroyed, or after IRB approval, transferred to another existing protocol. Final disposition of any samples cannot be done without written permission from the PI.

8.5 Reporting the Loss or Destruction of Samples/Specimens/Data to the IRB:

- Any loss or unanticipated destruction of samples or data resulting in a violation that compromises the scientific integrity of the data collected for the study will be reported to the IRB.

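### Section 7.1 says the GMA data could not identify anyone, yet those data include an all-day location log tied to drug-use reports; re-identification through location is not named as a risk

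*Combined protocol and SAP*

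**What the plan says.** Section 6.6 offers GMA to all Phase 2 participants (101 to 200) as an optional, exploratory component. From the phone's GPS log, "we will collect data on participants' locations throughout the day to assess how changes in environment affect mood and activities". It explains that, with assisted GPS, "smartphones can provide accurate location information more quickly than standalone GPS units", including indoors and among tall buildings. The method combines ecological momentary assessment "with GPS of self-reported data on craving, drug use, and stressors collected daily in real time via a cell-phone based application". Prompts come four times a day from Day 0 to Week 24, then "one-time daily from Week 25-48 to complete an assessment of drug use, craving, stress" and other factors. Phones are handed out on Day 0, and participants "will return their cell phones at Week 48".

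Section 7.1 has a paragraph on the risks of the phone and GMA. It says carrying the phone may be annoying or embarrassing. It says the phone gathers personal information and location, which are neither displayed on it nor linked to identifiers. It describes a PIN, regular transfer to password-protected computers at NIDA, and a secure server. It then states: "The data does not contain information that could be used to identify participants".

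Section 8.2 limits access to samples and data to investigators and study staff. Under its GMA heading it says some data will be shared with NIH partners as a collaboration agreement specifies, and adds: "There will be no participant identifiers in the shared data".

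**The concern.** The sentence in 7.1 says more than that names are left out. It says nothing in the data could be used to identify a participant. An accurate log of where someone is through the day shows where that person sleeps, works and goes for care. Removing names and contact details does not take that information away.

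Three features raise the stakes. The location record is joined to reports of illicit drug use. The group is small, and its screening sites are named in Section 6.1. Section 4.4 acknowledges high rates of incarceration among people who use drugs, so exposure could do real harm. Section 7.1 itself puts loss of confidentiality among the study's main risks, but its GMA paragraph does not say that location is a route to it.

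The sentence could also mislead those who handle the data. Section 9.3.1 makes a breach of confidentiality reportable within 5 business days. Staff who rely on 7.1 might not recognise exposure of coordinates as such a breach.

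**Working it through.** No sample-size, power or error-rate figure bears on this point. The check sets the sections side by side, with arithmetic only for the scale.

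**Consistency of the statement**

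1. What is collected: 6.6 gives location through the day, and 7.1 repeats that location is collected.
2. How precise it is: 6.6 calls the location information accurate, including where GPS signals are weak.
3. What it is joined to: 6.6 gives craving, drug use and stressors.
4. What is done to the coordinates: no section describes coarsening, masking or removing them. The measures in 7.1 (PIN, passwords, coded records, secure server, transfer off the phone, no names or contact details in electronic data) control who can reach the data. They do not change what the data reveal.
5. What 7.1 concludes: nothing in the data could identify a participant. Items 1 to 4 contradict this.

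**Named risks.** For GMA, 7.1 names annoyance and embarrassment. A general paragraph in 7.1 covers loss of confidentiality, with privacy at visits, coding and locked or password-protected records as the remedies. Neither paragraph mentions re-identification through location.

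**Scale**

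- People: participants 101 to 200, so at most 200 − 100 = 100. This is a ceiling, because GMA is optional.
- Time the phone is held: Day 0 to Week 48, which is 48 × 7 = 336 days.
- Prompts: 24 × 7 × 4 = 672, plus 24 × 7 × 1 = 168, gives up to 840 per participant.
- Cross-check with Section 11: the top payment tiers are 28 prompts a week (4 × 7) and then 7 a week (1 × 7). The payments are 24 × $20 = $480, 24 × $10 = $240, and $200 for returning the phone. They sum to $920, the stated maximum. The 48-week prompt schedule is therefore internally consistent.
- GPS duration: not stated. The 48 weeks above apply to the prompts and to holding the phone. Applying them to GPS logging is an assumption. If logging ran only during the four-a-day period, it would last 24 × 7 = 168 days.

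**The case against.** The best defence is that the sentence follows the one on transferring responses to NIDA, so the data it refers to may be the survey answers alone, or data stripped of direct identifiers. That reading is strained. Location was introduced earlier in the same paragraph as something the phone collects, and no section exempts or masks it.

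A reader might go further and infer that raw coordinates are released to NIH as de-identified data. The documents do not support this. Section 8.2 shares only some data, as defined by an agreement that is not in the documents, so we cannot tell whether coordinates are shared, coarsened or withheld. The promise of no identifiers could equally be meant to exclude them. Transfer to the NIDA server is not plainly a release to outsiders either. Section 6.6 says the assessments are evaluated by sub-investigators on this protocol, 8.2 limits access to investigators and study staff, and Section 8 requires IRB approval before other investigators receive samples or data.

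A reader might also infer that the location data are unprotected. They are not, because the access controls listed in 7.1 apply. What participants are told about location cannot be judged, since the consent pages are not available for review.

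Finally, keeping coordinates out of every analysis file would be only one possible arrangement, and a debatable one. It could constrain the stated aim of relating environment to mood and activities. That objection stands, and the fix does not ask for it.

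**Conclusion.** The statement in 7.1 is wrong as written, and re-identification through location is missing from the GMA risks. This rests on the documents' own description of the data and on one step of reasoning: an accurate all-day location trace can point to a person without a name.

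It affects at most 100 participants. Exposure of up to 48 weeks (336 days) each assumes that GPS logging lasts as long as the phone is held. No conclusion is drawn about what is actually shared under the collaboration agreement.

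GMA is optional and exploratory, and the SVR12 analysis and the sample size do not change. Severity is low to moderate. It is still worth correcting, because people deciding whether to join an optional component need an accurate account of its risk.

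**What to change.** 1. In 7.1, replace the sentence with one saying that names and contact details are not held with the GMA data, but that a participant's location history could identify them.
2. In the GMA risk paragraph, list re-identification through location beside annoyance and embarrassment.
3. Classify raw coordinates as identifiable data, with access limited to the study's own GMA investigators. They can then still carry out the environment-and-mood analysis.
4. In 8.2, state that the promise of no participant identifiers covers raw coordinates and home location in any file shared beyond those investigators. State also whether coordinates are among the data the collaboration agreement covers.
5. In 6.6, state when GPS logging starts and stops.

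The cost is protocol wording and a processing step before wider sharing. If the executed agreement does cover coordinates, it may need to be aligned with the new wording; the documents do not show whether that is so.

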7.2 Potential Benefits

Subjects may be cured of hepatitis C during the course of this study. Further, they may have decreased risk of HIV acquisition and may decrease or abstain from opioid misuse. They will contribute to the body of scientific research on treatment of hepatitis C and prevention of HIV in high-risk populations and therefore may confer long term benefits on other patients within their community. It is possible that subjects will receive no benefit from the study participation.

8 Stored Samples and Future Research

We will study the viral and host immunity to HCV and HIV in all patients. The results will be used to characterize each individual with regards to immune status and chronicity of disease. Studies on research samples may include the following:

A] HCV genome sequencing may be performed on plasma using the protocol as described and compared for variability and relatedness of sequences.

B] We will screen sera from all patients for differential expression of protein using multiplex cytokine arrays, which has the capability of detecting several different cytokines and other biologically relevant proteins.

C] We will perform detailed phenotypic and functional evaluation of immune cell types in the periphery. This will help us in determining the nature of antiviral immune responses in patients who are chronically infected, achieve SVR and acquire new HCV and HIV infections. Determination of specific immune defects in these individuals are important milestones in deciding future therapeutics and protective immunity to reinfection. Exhaustion and activation markers on T, B and NK cells will be quantified. Specific immune responses against pooled HCV peptides will be performed using an ELISPOT assay and/or flow cytometry.

Future use of the specimens will be based on the scientific merit of the investigation and would be decided by the Principal Investigator. They would be related to the study of HCV and/or HIV. Other investigators may wish to study these samples and/or data. In that case, IRB approval must be sought prior to any sharing of samples and/or data. Any clinical information shared about the sample would similarly require prior IRB approval. If approved, and once a Material Transfer Agreement (MTA) has been established, the study team may send de-identified samples to the collaborators. Investigators will use stored samples only for research.

8.1 Intended Use:

Some blood samples may be stored for future analysis in this research study. These samples will be stored by the IHV researchers and may be used in future research to learn more about HCV and HIV, the immune system and/or other related medical conditions. The blood will be used over time to gain a better understanding of the pathogenesis of HCV and HIV. Genetic testing will be performed. Different analytical and laboratory methods will be employed including but not limited to: PCR, ELISA, ELISPOT and immunohistochemistry; RNA/DNA, cytokine and antibody quantitation; viral particle detection and identification of genetic markers. The consent will include language for specimen storage.

8.2 Storage:

Samples will be kept in secure facilities with limited access. Samples and data will be stored using a unique identifier. Only investigators and study staff will have access to the samples and data.

GMA Data - Electronic data will be stored on secure password-protected computers. UMB has an executed Collaboration Agreement dated 5/1/18 with the National Institute on Drug Abuse (NIDA), National Institutes of Health (NIH) and will share some data as specified in the agreement with our scientific research partners at NIH. There will be no participant identifiers in the shared data.

8.3 Tracking:

Extra blood samples will be stored using a unique identifier that only the study team can trace back to the participants. These stored samples as well as a linkage file will be maintained in a database that will be managed by the Investigators and/or Study Coordinators and will be maintained on the IHV server. This database will also be stored on the password-protected computer of the Lead-Investigator/Study Coordinator in an encrypted and/or password-coded file.

8.4 Disposition at the Completion of the Protocol:

At the completion of the protocol (termination), samples and data will either be destroyed, or after IRB approval, transferred to another existing protocol. Final disposition of any samples cannot be done without written permission from the PI.

8.5 Reporting the Loss or Destruction of Samples/Specimens/Data to the IRB:

- Any loss or unanticipated destruction of samples or data resulting in a violation that compromises the scientific integrity of the data collected for the study will be reported to the IRB.
- Participants may request at any point not to have their samples stored. In this case, the Principal Investigator will destroy all known remaining samples and report what was done to

both the participant and to the IRB. This decision will not affect the subject's participation in any other protocols.

Generally, the results from the research stored samples will not be given to the participant's primary care provider or appear in the medical record. This is because the test results, unlike routine medical testing, may be experimental or preliminary. The relevance of these tests to direct patient care may be unknown. At the participant's request, the results of any research tests will be discussed with the primary care physician by the Investigators.

9 Assessment of Safety

As this is an observational study involving standard of care treatment, with interventions limited to non-standard care blood draws and epidemiologic information collection, safety issues are not expected. Only those reportable Adverse Events (AEs) related to the research procedures will be reported. The PI will review the safety data and report any unexpected events to the IRB along with annual continuing review

9.1 Recording/Documentation

At each contact with the patient, information regarding adverse or unexpected events related to research procedures will be elicited by appropriate questioning and examinations and will be immediately recorded on a source document. Source documents will include: progress notes, laboratory reports and data collection tools. Source documents will be reviewed in a timely manner by the research team.

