9.2 Definitions

Adverse Event: Any untoward medical occurrence in a human subject, including any abnormal sign, symptom, or disease, temporally associated with the subject's participation in research, whether or not considered related to the subject's participation in the research.

Protocol Deviation: Any change, divergence, or departure from the IRB approved study procedures in a research protocol. Protocol deviations are designated as serious or non-serious and further characterized as:

- Those that occur because a member of the research team deviates from the protocol.
- Those that are identified before they occur, but cannot be prevented.
- Those that are discovered after they occur

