9.4 Annual Reporting to the IRB

The following items will be reported to the University of Maryland IRB in summary at the time of Continuing Review:

- Serious adverse events or deaths that are not related to the research
- All adverse events associated with research including expected AEs Protocol deviations. This includes AEs related to phlebotomy within 48 hours of procedure.
- Serious, continuing, and minor non-compliance
- Any trends or events which in the opinion of the investigator should be reported
- Any study participants incarcerated while on active HCV treatment that were provided their remaining HCV medications in the jail/prison

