9.4.1 Type and Duration of the Follow-up of Subject after Adverse Events

All SAEs and non-serious AEs identified in this study will be followed until resolution or until the PI judges the AE/SAE has stabilized and no more follow-up is required. This requirement indicates that the follow-up may be required for some events after the participant discontinues participation from the study. These events will be reported to the IRB annually.

10 Withdrawal of a Subject

A participant may withdraw from the study at any time. As part of their duties to ensure that research participants are protected, the IRB, IIV, or other government agencies may discontinue the study at any time. Voluntary withdrawal from the protocol may occur at any time at the request of either the participant or the PI. If a request is made to withdraw from the protocol, all further planned study procedures will be immediately cancelled and further follow-up will be terminated. Samples and data collected already collected may be used.

If a patient becomes pregnant during the course of the study, the patient will be discontinued from the study.

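### Section 9.1 asks only about events tied to research procedures, so the unrelated SAEs and deaths that Section 9.4 must report would be counted only when staff happen to learn of them

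*Combined protocol and SAP*

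**What the plan says.** Two provisions are narrow:

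- Section 9.1 sets what staff ask at each contact: "information regarding adverse or unexpected events related to research procedures will be elicited by appropriate questioning and examinations".
- The opening of Section 9 limits reporting in the same way: "Only those reportable Adverse Events (AEs) related to the research procedures will be reported". Sections 9 and 12 describe the research interventions as blood draws and data collection.

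Three are wider:

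- Section 9.2 defines an adverse event as "Any untoward medical occurrence in a human subject, including any abnormal sign, symptom, or disease", and applies this "whether or not considered related to the subject's participation in the research".
- Section 9.4 lists, among the items for the annual IRB summary, "Serious adverse events or deaths that are not related to the research".
- Section 9.4.1 states: "All SAEs and non-serious AEs identified in this study will be followed until resolution" or until the PI judges the event stable.

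Section 9.3 also sends deaths from the natural history of hepatitis to continuing review. Section 12 provides for weekly safety monitoring by the PI and study team, with reporting as in Section 9.

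**The concern.** The question put to the participant is narrower than the report the protocol promises. A site that follows 9.1 exactly asks about a bruise or a faint after phlebotomy. It is not told to ask about a hospital admission or any other serious event from another cause. Relatedness is normally judged after an event is known; here it decides what is asked.

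At stake is how the weekly review and the annual IRB report can be read. If few unrelated SAEs or deaths are listed, nobody can say whether few occurred or few were noticed. Sections 9 and 12 state that safety problems are not anticipated, and a short list would seem to confirm this without testing it. There is a smaller link to the primary endpoint. Section 13.1 counts treated patients without follow-up data as failures, so a participant who dies before SVR12 enters the primary result as a failure, with no planned step to find out about the death.

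**Working it through.** The plan states no figure on this point, so the check is mainly a comparison of sections.

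1. **Duty.** Section 9.4 requires unrelated SAEs and deaths to be summarised each year. Section 9.3 adds hepatitis-related deaths.
2. **Active collection.** Section 9.1 is the only instruction on eliciting events, and it covers research-procedure events alone. The Section 9 sentence on reporting, read literally, excludes what 9.4 demands.
3. **Schedule.** Appendix B has no row for AEs, SAEs or vital status. HCV physician visits fall at screening, Day 0 and weeks 4, 8, 12 and 24. Follow-up runs to week 96, so the span without one is 96 − 24 = 72 weeks, and 72/96 = 75% of follow-up.
4. **Optional tracks.** PrEP and buprenorphine physician visits run to 48 weeks after their own start, which may be as late as week 24. The latest possible visit is therefore at 24 + 48 = week 72. Even these participants have no physician visit scheduled in the final 24 weeks, and those who take neither treatment have none after week 24.
5. **Passive routes.** Section 9.1 says "Source documents will include: progress notes, laboratory reports and data collection tools", and the research team reviews them. Section 6.7 documents the reason for any early termination. Section 6 provides for contact after a missed visit under each clinic's own procedure. Any of these may bring an event to light; none requires anyone to ask about SAEs or to establish vital status. Section 9.4.1 covers events once identified and does not say how unrelated ones are identified.
6. **Overdose.** Section 6.6 describes people who continue to use drugs during treatment as at "risk for harm including overdose, acquiring or transmitting HIV, HCV, and other diseases", and names overdose among the topics the GMA will explore. The GMA is optional, limited to Phase 2 (100 of 200 participants) and ends at week 48 of 96. If every Phase 2 participant joins and completes it, coverage is (100 × 48)/(200 × 96) = 4,800/19,200 = 25% of planned participant-weeks. Phase 1, the primary efficacy cohort, has none.

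**Scale, on an assumed rate only.** The documents give no SAE rate. With complete follow-up, exposure is 200 × 96/52.18 ≈ 368 person-years. At an assumed 5 to 20 serious events per 100 person-years, that gives 368 × 0.05 ≈ 18 to 368 × 0.20 ≈ 74 events. The conclusion does not depend on this range.

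**The case against.** The best defence is that this is an observational study of approved drugs given as standard of care. Limiting AE questioning to what the research adds is a reasonable choice, and 9.4 can be read as covering events that become known. Physician visits, progress notes, laboratory reports, concomitant-medication records and early-termination reasons are all routes by which serious events reach the team.

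Much of this stands. Narrow collection of non-serious AEs is acceptable, and unrelated events would not go wholly unseen. But if 9.4 means only known events, the counts have unknown completeness, and the reporting sentence in Section 9 still has to be reconciled with 9.4.

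A reader might infer more than the documents support:

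- *That overdose is never collected.* Overdose is a named GMA topic, and the contents of Appendices C, D, G and J are not shown, so the absence of overdose questions cannot be established. Section 6.6 also attaches no safety-reporting duty to it. What can be said is that no section provides for collecting it as a safety event.
- *That 9.1 conflicts with Section 4.3.1 or 6.2.* The greater-than-minimal-risk statement in 4.3.1 explains why children are excluded. Section 6.2 describes standard-of-care treatment, which fits the framing in Section 9.
- *That deaths cannot be separated from virologic failure or drop-out.* HCV RNA identifies virologic failure, and Section 6.7 documents reasons for early termination. The gap concerns deaths and SAEs among participants with no data.
- *That wider questioning at visits would capture deaths.* A participant cannot report their own death; that needs the missed-visit route.

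**Conclusion.** The point holds as a mismatch between a stated rule and a stated duty. Followed as written, 9.1 and the reporting sentence in Section 9 cannot be relied on to produce the summary of unrelated SAEs and deaths that 9.4 requires, and nothing else in the protocol fills the gap. The counts would depend on incidental awareness, which is weakest after week 24, when 75% of follow-up remains and no HCV physician visit is scheduled.

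The number of events missed cannot be derived from the documents; 18 to 74 is the number that would occur, not the number missed, under an assumed rate and complete follow-up. The SVR12 estimate does not change, because failures for missing data are scored the same way whatever the cause. The effect is on the completeness and interpretation of the safety record, and on how those failures can be explained. The change should be made, but it is not critical to the primary analysis. This rests on reading Appendix B and the sections as provided; survey contents could not be checked.

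**What to change.** Reconcile Sections 9, 9.1 and 9.4:

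- **(a)** Amend 9.1 so that at each scheduled study visit through week 96 staff ask about and record SAEs, including hospitalisations and serious overdose, regardless of relatedness. Keep non-serious AE collection limited to research procedures. Section 9.2 defines an adverse event but not a serious one, so add that definition, and add a matching row to Appendix B.
- **(b)** Use the missed-visit contact procedure in Section 6 to record vital status, and cause of death where known.
- **(c)** Reword the restrictive reporting sentence in Section 9 to agree with 9.4.
- **(d)** In the SVR12 report, list known deaths and SAEs before SVR12 beside the participants scored as failures for missing data. The 13.1 scoring rule stays as it is.

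Section 4.4 bars study data collection during incarceration and Section 10 ends follow-up at withdrawal. Those limits can remain, but the annual summary should state them.

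The cost is a wording amendment, a short form taking a few minutes at visits already planned, and a longer annual report. Treatment, endpoint and sample size are untouched.
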